6.4.1 Analyses of Primary Efficacy Parameter

The primary efficacy parameter (PASI-75 response rate at EOT) will be compared for each JTE-451 dose group with placebo using the Cochran-Mantel-Haenszel (CMH) test, stratified by prior exposure to biologic therapy (Yes or No) and body weight (<90 kg or \geq 90 kg at Visit 2). The adjusted odds ratio for each active treatment group to the placebo group along with 95% CIs and p-value will be reported.

A sample SAS code as below:

- Cochran-Mantel-Haenszel test (Run by K=2, 3 separately):

```
PROC FREQ DATA=;
  TABLES <biologic therapy> * <body weight> * <TRTn> * <PASI75> / CMH;
  WHERE <TRTn> IN (1, K);
RUN;
```

Note:

- <biologic therapy>=0 represents ‘Biologic-naïve’;
<biologic therapy>=1 represents ‘Biologic-experienced’;
- <body weight>=0 represents ‘Body weight < 90 kg’;
<body weight>=1 represents ‘Body weight \geq 90 kg’;
- <TRTn>=1 for placebo, <TRTn>=2 for JTE-451 200 mg, <TRTn>=3 for JTE-451 400 mg,
- <PASI75>=0 represents a non-responder, <PASI75>=1 represents a responder;

In addition, logistic regression model-based supportive analyses will be performed for the pairwise comparisons between JTE-451 and placebo groups (as shown in Model 1 below) and for the evaluation of dose response relationship (as shown in Model 2 below). The logistic regression models will include baseline PASI value and two stratification factors (prior biologic therapy and body weight) as covariates.

Sample SAS codes as below:

- Model 1 (pairwise treatment vs placebo comparison)

```
PROC LOGISTIC DATA= DESCENDING;
  CLASS <biologic therapy> <body weight>;
  MODEL <PASI75> = <Dose_200> <Dose_400> <Baseline X>
    <biologic therapy> <body weight>;
RUN;
```

- Model 2 (dose-response analysis)

```
PROC LOGISTIC DATA= DESCENDING;
  CLASS <biologic therapy> <body weight>;
```

```
MODEL <PASI75> = <Dose> <Baseline X>
  <biologic therapy> <body weight>;
ODDSRATIO <Dose>;
RUN;
```

Note:

- In Model 1, $\langle Dose_x \rangle = 1$ if dose=x; otherwise. $\langle Dose_x \rangle = 0$; i.e., $\langle Dose_x \rangle$ is a dummy variable.
- In Model 2, $\langle Dose \rangle = 0, 200, 400$ for placebo and each JTE-451 dose level, respectively.
- $\langle Baseline X \rangle$ denotes baseline PASI value.
- $\langle PASI75 \rangle = 1$ represents a responder; $\langle PASI75 \rangle = 0$ represents a non-responder.
- $\langle biologic therapy \rangle = 0$ represents ‘Biologic-naïve’;
 $\langle biologic therapy \rangle = 1$ represents ‘Biologic-experienced’;
- $\langle body weight \rangle = 0$ represents ‘Body weight < 90 kg’;
 $\langle body weight \rangle = 1$ represents ‘Body weight >= 90 kg’;

From the model fitting, one obtains adjusted odds ratios and corresponding p-values for the respective pairwise treatment comparison versus placebo.

6.4.2 Analyses of Secondary Efficacy Parameters

For dichotomous secondary efficacy parameters at defined single time point, similar analyses used for the primary efficacy parameter above will be performed as appropriate. For assessing dichotomous efficacy parameter measured at multiple time points, a generalized estimating equation (GEE) method on the logit scale will be used. The model includes effects for treatment, time, treatment by time interaction, stratification factors, appropriate baseline and subject as the repeated factor. The odds ratio (OR) of each JTE-451 dose group relative to placebo at the same time point will be estimated.

A sample SAS code as below:

- Model: (Generalized estimating equation (GEE) method on the logit scale)

```
PROC GENMOD DATA=;
  CLASS <usubjid> <visit>(REF="Week 0") <TRTn>(REF=1)
    <biologic therapy>(REF =0) <body weight>(REF =0);
  MODEL <SAPE> = <TRTn> <visit> <TRTn>*<visit> <Baseline> <biologic therapy> <body weight >
    /DIST=BINOMIAL LINK=LOGIT;
  REPEATED SUBJECT=<usubjid>(<TRTn>) / TYPE=UN CORRW;
RUN;
```

Note:

- $\langle usubjid \rangle$ denotes subject ID;
- $\langle SAPE \rangle$ denotes any dichotomous efficacy parameter;
- $\langle TRTn \rangle = 1$ for placebo, $\langle TRTn \rangle = 2$ for JTE-451 200 mg, $\langle TRTn \rangle = 3$ for JTE-451 400 mg;
- $\langle Baseline \rangle$ denotes appropriate baseline corresponding to the efficacy parameter;
- $\langle biologic therapy \rangle = 0$ represents ‘Biologic-naïve’;
 $\langle biologic therapy \rangle = 1$ represents ‘Biologic-experienced’;
- $\langle body weight \rangle = 0$ represents ‘Body weight < 90 kg’;
 $\langle body weight \rangle = 1$ represents ‘Body weight >= 90 kg’;

For assessing the continuous efficacy parameter measured at multiple time points, a mixed effect model with repeated measures (MMRM) will be used. The model includes fixed effects for treatment, time, treatment by time interaction, stratification factors, appropriate baseline and

measurements within each subject as repeated measures. The treatment difference of each JTE-451 dose group relative to placebo at the same time point will be estimated as well as the corresponding 95% CI.

A sample SAS code is displayed below:

- Model: (Mixed-effect model with repeated measures (MMRM))

```
PROC MIXED DATA=;
  CLASS <usubjid> <visit> <TRTn>(REF=1) <biologic therapy>(REF =0) <body weight >(REF =0);
  MODEL <PCHG> = <Baseline> <TRTn> <visit> <TRTn>*<visit>
    <biologic therapy> <body weight >;
  REPEATED/SUBJECT=<usubjid>(<TRTn>) TYPE=UN;
  LSMEANS <TRTn>/PDIFF CL;
  RUN;
```

Note:

- <PCHG> denotes change from baseline or percent change from baseline in any continuous efficacy parameter;
- <TRTn>=1 for placebo; <TRTn>=2 for JTE-451 200 mg; <TRTn>=3 for JTE-451 400 mg;
- <Baseline> denotes appropriate baseline corresponding to the efficacy parameter;
- <biologic therapy> =0 represents ‘Biologic-naïve’;
- <biologic therapy> =1 represents ‘Biologic-experienced’;
- <body weight>=0 represents ‘Body weight < 90 kg’;
- <body weight>=1 represents ‘Body weight >= 90 kg’;

The assessments from the follow-up visit and derived EOT will not be included in the GEE or MMRM models.

[figure not shown]
The Itch NRS scores will be summarized descriptively by each JTE-451 dose group and placebo group, and analyzed in an MMRM for weekly averages (by-visit only) as described above.

Observed values and changes from the weekly average at one week prior to Week 0 to the weekly average at one week prior to each scheduled visit which includes the day of scheduled visit and a 6-day collection before the scheduled visit will be derived and analyzed by each study visit from Week 0 to the Follow-up visit (including EOT) using both the ITT and PP populations, respectively. The data used for by-visit average score derivation in the treatment period (not including the Follow-up visit) will be up to the day of last dose plus 4 days. For the Follow-up visit, the weekly average will use the collection at the day of Follow-up visit and the 6-day collection before the Follow-up visit.

In addition, the Itch NRS scores will be derived and analyzed by each JTE-451 dose group and placebo as following:

- Observed values and changes from baseline (one week prior to Week 0) in weekly average score will be analyzed by each week from Week 0 to Week 20 using the ITT population only. For early-terminated subjects, the data used for weekly average score derivation will be up to the day of last dose plus 4 days.

- Descriptive statistics of observed values and changes from Day 1 in daily score will be presented by each day from Day -6 to Day 28 using the ITT population only. For early-terminated subjects, the data used for daily score summary will be up to the day of last dose plus 4 days.

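### The GEE sample code in SAP 6.4.2 does not set the modelled response level; under the SAP's only stated responder coding, odds ratios built on it would be for non-response

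*SAP*

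**What the plan says.** SAP 6.4.1 (primary endpoint) gives the responder coding: "<PASI75>=0 represents a non-responder, <PASI75>=1 represents a responder". The CMH program uses "TABLES <biologic therapy> * <body weight> * <TRTn> * <PASI75> / CMH", with placebo as treatment 1, and the text says "The adjusted odds ratio for each active treatment group to the placebo group along with 95% CIs and p-value will be reported". Both supportive logistic programs open with "PROC LOGISTIC DATA= DESCENDING".

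SAP 6.4.2 sends binary secondary endpoints at a single time point to the same kind of analysis as the primary. For repeated binary measurements it specifies a GEE. That sample program opens "PROC GENMOD DATA", uses the options "DIST=BINOMIAL LINK=LOGIT", and makes placebo the treatment reference. It has neither DESCENDING nor an event or reference option on the response. Its notes say only that the response variable `<SAPE>` "denotes any dichotomous efficacy parameter"; they give no 0/1 coding. The stated aim is: "The odds ratio (OR) of each JTE-451 dose group relative to placebo at the same time point will be estimated".

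SAP 6.4.2 leaves the follow-up visit and the derived EOT value out of the GEE. SAP section 8 names SAS 9.4 or higher.

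**The concern.** The plan's other programs point one way: the CMH table and both logistic models give an odds ratio for response, so values above 1 favour JTE-451. The GEE program lacks the keyword that gives the logistic models this direction. Run under the same coding, it would describe the odds of not responding.

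The endpoints affected are listed secondary parameters in SAP 5.2.2: PASI-50, PASI-75, PASI-90 and sPGA 0 or 1 over time. SAP 6.4 asks for treatment effects with 95% confidence intervals to be tabulated. SAP 6.4.7 treats agreement between the by-time-point results and the multiple-time-point results as supporting the findings. If one set is for response and the other for non-response, an effective dose would show an odds ratio above 1 in one table and below 1 in the other. The p-values do not change, so a check on significance alone would not reveal the reversal.

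**Working it through.** The plan states no figure to reproduce here; the question is which way each program points.

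**1. CMH program.** In each stratum the rows are placebo then active, and the columns are 0 (non-responder) then 1 (responder). The odds ratio is OR = (n11 × n22) / (n12 × n21). The SAP gives no response rates, so the counts below are assumptions, with 50 per arm as planned:

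- 5/50 placebo, 15/50 active: (45 × 15) / (5 × 35) = 675/175 = 3.86
- 5/50 placebo, 20/50 active: (45 × 20) / (5 × 30) = 900/150 = 6.00

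These equal the odds of response on active divided by the odds on placebo; for example (20/30) / (5/45) = 6.00. Values above 1 favour JTE-451.

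**2. Logistic programs.** DESCENDING with 0/1 coding models the probability of 1, which is response. The direction is the same as in the CMH analysis.

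**3. GEE program.** For a single binary response variable without DESCENDING or EVENT, PROC GENMOD models the lowest ordered level. This is default behaviour of the named software and is not stated in the documents. If `<SAPE>` is coded like `<PASI75>`, that level is 0, non-response. With placebo as the treatment reference, the contrast gives:

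- 5/50 vs 15/50: (35/15) / (45/5) = 0.259 = 1/3.86
- 5/50 vs 20/50: (30/20) / (45/5) = 0.167 = 1/6.00

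**4. Simulated GEE.** One simulated trial of 3 × 50 subjects at Weeks 8, 12 and 16 was fitted twice with a logit GEE, once to response and once to non-response. The model had treatment, visit, their interaction, baseline and both stratification factors. Assumed true response rates at the three visits were 8%, 10%, 10% on placebo; 18%, 22%, 25% on 200 mg; and 25%, 35%, 40% on 400 mg. An exchangeable working correlation was used in place of the SAP's unstructured one.

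| Contrast with placebo | Modelling response | Modelling non-response | p, both fits |
|---|---|---|---|
| 200 mg, Week 16 | 3.116 (1.007 to 9.647) | 0.321 (0.104 to 0.994) | 0.0487 |
| 400 mg, Week 12 | 5.219 (1.583 to 17.211) | 0.192 (0.058 to 0.632) | 0.0066 |
| 400 mg, Week 16 | 6.293 (2.099 to 18.862) | 0.159 (0.053 to 0.476) | 0.0010 |

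All six dose-by-visit odds ratios inverted, with their limits exchanged and inverted (1/18.862 = 0.053; 1/2.099 = 0.476). The simulation illustrates the reversal; its estimates are not forecasts for this trial.

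**The case against.** The strongest reply is that this is sample code with placeholders, while the governing text names the intended contrast correctly. The sample has no LSMEANS or ESTIMATE statement, so it prints no by-visit odds ratio; a programmer has to add one and could notice the modelled level while doing so. SAP section 8 puts analyses under quality control, and the mock tables, which may label the direction, are in a separate document. Response frequencies by treatment over time (Protocol 3.8.4.2) and graphs (SAP 6.4) would visibly conflict with a reversed odds ratio. The coding of `<SAPE>` is not stated, and the software default is not in the documents.

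Most of this stands as a limit on scope. A reader might infer that every by-visit odds ratio in the report will come out inverted. The documents do not support that: single-time-point analyses use the correctly oriented CMH and logistic programs, EOT and follow-up are outside the GEE, and the reversal depends on how `<SAPE>` is coded. Nor do they support reading the issue as a threat to the primary result or to any p-value.

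The reply does not remove the point. The text says active relative to placebo but does not say odds of what. The only responder coding in the SAP, applied to the program as printed, gives the wrong direction. Adding an odds-ratio statement to that program would not change the modelled level. Later checks may catch the error, but the plan should not rely on them.

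**Conclusion.** The point holds in conditional form. If `<SAPE>` is coded 1 for responder and 0 for non-responder, the GEE program as printed models non-response. Any JTE-451-versus-placebo odds ratio and confidence interval derived from it at the treatment-period visits is then the exact reciprocal of the GEE odds ratio for response. It need not be the exact reciprocal of the CMH or logistic estimate at the same visit, because adjustment and missing-data handling differ, but it would read in the opposite direction to them.

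The conclusion rests on two things outside the SAP's explicit text: that the coding carries over from `<PASI75>`, and the default response level of PROC GENMOD. The evidence within the SAP is that DESCENDING is present in both logistic programs and absent from the GEE program. This is a mismatch between sample code and intent that affects how secondary results are presented. It should be corrected because the code as printed would mislead.

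**What to change.** In SAP 6.4.2, write `PROC GENMOD DATA=<input> DESCENDING;` or set the event on the response with `MODEL <SAPE>(EVENT='1') = ...`. Add to the notes that `<SAPE>` = 1 is a responder and `<SAPE>` = 0 a non-responder. An odds ratio above 1 then favours JTE-451 in the CMH, logistic and GEE outputs alike.

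The cost is one keyword and one note line. No data, sample size or test changes.

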3. STUDY DESIGN

This is a 16-week, multicenter, randomized, double-blind, placebo-controlled, parallel-group study in subjects with moderate to severe plaque psoriasis.

Eligible subjects will be randomized at Visit 2 to receive JTE-451 200 mg twice a day (BID) (400 mg/day), 400 mg BID (800 mg/day) or placebo BID for 16 weeks. Approximately 150 subjects are planned to be randomized into 3 treatment groups. Randomized subjects will visit the site at Weeks 2, 4, 8, 12 and 16 during the treatment period. A follow-up visit will take place approximately 4 weeks after the last dose of study drug. Randomization will be stratified based on prior exposure of subjects to biologic therapy (i.e., biologic-naïve vs. biologic-experienced subjects) and body weight (i.e., <90 kg vs. ≥90 kg at Visit 2).

The study duration will be of approximately 24 weeks per subject:

- Up to 28-day Screening Period
- 16-week double-blind Treatment Period
- 4-week Follow-up Period

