6.4.7 Handling of Dropouts and Missing Data

There may be missing data intermittently (e.g., a missing visit or subject dropout). For PASI-50/-75/-90 and sPGA (achieving score of 0 or 1) responses, subjects with missing EOT data will be imputed as non-responders at EOT; for analyses by scheduled time points, missing data will not be imputed. For analysis with multiple time points, any missing data will be imputed using the last observation carried forward (LOCF) method. For parameters analyzed both by time point and with multiple time points, these two approaches would strengthen the findings when they are similar.

For efficacy analysis of continuous parameters, missing data will not be imputed. This is because the statistical models employed (e.g., mixed effect model) generally provide valid estimates if the missing data mechanism is so-called “missing at random,” a common assumption made as the first approach for analysis.

For the Itch NRS, 4 completed days are necessary to derive a weekly score (1-3 missed days, consecutive or non-consecutive, are allowed). Any missing individual items are treated as missing data. When a weekly score in post-dose time point cannot be calculated (less than 4 completed days), the time point will not be included in the analysis. If a baseline weekly score cannot be derived (i.e., less than 4 completed days from Day -6 to Day 1), the Itch NRS score of the subject will not be included in the analysis.

For the Skindex-16, if more than 25% of the responses are missing, the scale is considered missing. An item with multiple answers is considered missing. The skindex-16 score will be derived for all study visits.

Additional sensitivity analyses of the primary efficacy parameter, i.e., PASI-75 at EOT, may be performed using other missing data handling procedures or approaches.

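### The MMRM sample code names no repeated effect, so an intermittent gap without a placeholder row attaches later values to the wrong visit's variance and covariance

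*SAP*

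**What the plan says.** SAP 6.4.2 analyses continuous efficacy parameters over time with an MMRM. The prose says only that the measurements within a subject are the repeated measures; the covariance structure appears only in the sample code.

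- Visit is declared as a class variable: "CLASS <usubjid> <visit> <TRTn>(REF=1) <biologic therapy>(REF =0) <body weight >(REF =0".
- Visit enters the mean model: "MODEL <PCHG> = <Baseline> <TRTn> <visit> <TRTn>*<visit>", followed by the two stratification factors.
- The covariance line is "REPEATED/SUBJECT=<usubjid>(<TRTn>) TYPE=UN", with no repeated effect.

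Five visits enter the model. SAP 3 states "Randomized subjects will visit the site at Weeks 2, 4, 8, 12 and 16 during the treatment period", and SAP 6.4.2 adds "The assessments from the follow-up visit and derived EOT will not be included in the GEE or MMRM models".

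SAP 6.4.7 expects gaps: "There may be missing data intermittently (e.g., a missing visit or subject dropout". It also says "For efficacy analysis of continuous parameters, missing data will not be imputed", and it leaves out any post-dose Itch NRS time point whose week has fewer than 4 completed diary days. No section of the SAP requires a row with a missing response for each missed visit, or sorting by visit within subject.

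**The concern.** TYPE=UN gives each visit its own variance and each pair of visits its own covariance, so the model must know which visit each record belongs to. Visit in the MODEL statement tells it which mean to use. It does not tell it which row and column of the covariance matrix to use. With no repeated effect, PROC MIXED takes the first record of a subject as position 1, the second as position 2, and so on.

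That is correct for complete records in visit order, and it fails when a middle visit has no record. The covariance determines the standard errors and, with incomplete data, the weights behind the estimates. SAP 6.4.7 justifies not imputing by the validity of the mixed model under missing at random. That argument presupposes a covariance matrix attached to the right visits. The analyses at stake are the continuous secondary ones: PASI and BSA percent change, and changes in sPGA, Skindex-16 and Itch NRS.

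**Working it through.** **No plan figure to reproduce.** The documents state no number that depends on this code, and the visible text gives no SD, correlation or skip rate.

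**Step 1. What the code does.** Let Σ be the 5 × 5 unstructured matrix for Weeks 2, 4, 8, 12 and 16. Subject i contributes the submatrix of Σ picked out by an index set p. It should be p = the visits attended. As coded, p = 1, 2, …, n for n records. For a subject with one missing visit and no row for it:

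| Visit without a row | Values misplaced | Week used → position taken |
|---|---|---|
| Week 2 | 4 | 4→2, 8→4, 12→8, 16→12 |
| Week 4 | 3 | 8→4, 12→8, 16→12 |
| Week 8 | 2 | 12→8, 16→12 |
| Week 12 | 1 | 16→12 |
| Week 16 | 0 | none |

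The last row shows why dropout is harmless: when records stop and nothing follows, the remaining positions are right. A simulation with 17.5% dropout and no skipped visits (assumed SDs 15, 20, 27, 32, 35; correlation 0.75 per 4 weeks) gave identical results under both codings, with a Week 16 model SE of 7.32 for each.

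**Step 2. Size when visits are skipped.**

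- From the documents: about 50 per arm, 1:1:1, five visits, 15–20% discontinuation (SAP 6.1; midpoint 17.5% used).
- Assumed: SDs rising from 15 to 34, AR(1) correlation 0.8, and skip rates of 2%, 5% and 10%.
- Quantity: the Week 16 difference, 400 mg BID against placebo, with a REML-type fit.

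There were two sets of runs: A with 800 trials per setting, B with 1,300–1,600.

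| Skipped | SE shortfall, row-order coding | Coverage, row order | Coverage, visit indexed |
|---|---|---|---|
| 2% | 1% (A and B) | near unchanged (A); 95.4% (B) | 96.1% (B) |
| 5% | 1 − 7.05/7.22 = 2.4% (A); 2.4% (B) | 93.1% (A); 94.3% (B) | 94.8% (A); 96.1% (B) |
| 10% | 1 − 6.91/7.23 = 4.4% (A); 4.5% (B) | 92.5% (A); 92.7% (B) | 94.6% (A); 95.5% (B) |

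The Monte Carlo standard error of coverage at 10% is √(0.925 × 0.075/800) = 0.9 points in A and at most √(0.927 × 0.073/1,300) = 0.7 points in B.

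**Step 3. Why coverage falls by more than the SE shortfall suggests.** At 10% skipped in set A, the true sampling SD of the estimate rises from 7.22 to 7.71 while the reported SE falls to 6.91. The ratio is 6.91/7.71 = 0.896. With a critical value of about 1.98, expected coverage is 2Φ(1.98 × 0.896) − 1 ≈ 92.4%, in line with the simulated 92.5%.

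**Step 4. Effect on the estimate.** Between the two codings, the estimate in a single trial moves by 1.0, 1.6 and 2.1 points on average at 2%, 5% and 10% skipped (largest move at 10%: 9.8). At 10% that is 2.1/7.23 = 0.29 of a standard error. The moves are scatter: in set B the mean bias of the two codings differed by 0.02 or less.

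**The case against.** **The harm is conditional.** It needs a gap followed by later data, and a dataset with no row for the gap. The only missingness rate in the plan is 15–20% discontinuation, which is mainly dropout and then harmless. Protocol 3.5.3 tells sites to rearrange late visits rather than skip them. The analysis dataset may keep a row per scheduled visit, which preserves the positions. All of this stands, and it limits the size. It does not remove the point: SAP 6.4.7 itself expects intermittent gaps, the itch diary rule can create them with no missed visit, and nothing in the SAP secures the row layout.

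**It is labelled sample code.** The same block requests least-squares means for treatment only, which does not give the by-visit differences that the prose requires, so it may be a skeleton. But it is the SAP's only covariance specification, and nothing in the prose would correct a programmer who followed it.

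**Stronger readings that a reader might infer.**

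- *The intervals and p-values of every continuous secondary endpoint are wrong.* The documents do not support this. With complete data, dropout only, or placeholder rows in visit order, the code gives the right answer.
- *The visit means are mislabelled or biased.* Visit is in the MODEL statement, so the means are labelled correctly, and the simulations showed extra noise rather than added mean bias.
- *The GEE model is equally affected.* Its line, "REPEATED SUBJECT=<usubjid>(<TRTn>) / TYPE=UN CORRW", also names no within-subject visit effect. But SAP 6.4.7 applies LOCF to analyses with multiple time points, which closes most gaps; a missed Week 2 is the exception, having no earlier post-baseline value. GENMOD's default empirical standard errors give further protection. The GEE was not simulated.

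The primary CMH comparison uses one EOT value per subject, with missing EOT data counted as non-response, and is untouched.

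**Conclusion.** The omission is plain on the face of the code and should be corrected. Its effect is limited to the continuous secondary MMRM analyses, and arises only for subjects with an intermittent gap and no ordered placeholder row. The direction is anti-conservative: the reported standard error shrinks while the estimate becomes more variable.

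The effect is negligible at 2% skipped visits, small at 5%, and about 2 to 3 points of coverage at 10%. These sizes rest on assumed SDs, correlation and skip rates, since the plan supplies only the sample size, visit schedule and discontinuation range. The finding of no added mean bias holds for the missingness simulated and is not claimed beyond it. The consequence for the trial's main conclusion is nil.

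**What to change.** In the PROC MIXED block of SAP 6.4.2, write `REPEATED <visit> / SUBJECT=<usubjid>(<TRTn>) TYPE=UN;`. Visit is already a class variable there, so this adds one variable name. It changes nothing when records are complete and in visit order, and it puts every value in its correct position otherwise.

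If the code is left as it is, the SAP should at least state that the input dataset holds one row per scheduled visit, sorted by visit within subject, with the response set to missing where there is no value. Naming the effect is safer, because it does not depend on a dataset convention.

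Adding `WITHINSUBJECT=<visit>` to the PROC GENMOD REPEATED statement is optional tidying. Neither change affects the study's conduct or data collection.

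### The MMRM sample code in SAP 6.4.2 requests one visit-averaged difference per dose, where the text promises a difference at each time point

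*SAP*

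**What the plan says.** SAP 6.4.2 sets out two repeated-measures analyses for the secondary parameters.

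- **Continuous parameters (MMRM).** "The treatment difference of each JTE-451 dose group relative to placebo at the same time point will be estimated", with a 95% CI. Protocol 3.8.4.2 says the same of its mixed model and adds a linear trend test at each time point.
- **Dichotomous parameters (GEE on the logit scale).** "The odds ratio (OR) of each JTE-451 dose group relative to placebo at the same time point will be estimated".
- **Visits modelled.** "The assessments from the follow-up visit and derived EOT will not be included in the GEE or MMRM models". SAP 5.2.2 lists Weeks 2, 4, 8, 12, 16, 20 and EOT for the secondary parameters.

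The MMRM program is introduced with "A sample SAS code is displayed below". It fits `<TRTn>`, `<visit>` and `<TRTn>*<visit>`. Its REPEATED statement gives the subject and TYPE=UN but names no repeated effect. Its one estimate statement is "LSMEANS <TRTn>/PDIFF CL".

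The GEE program fits the same interaction and stops after its REPEATED statement. It has no LSMEANS, ESTIMATE or odds-ratio request. It describes its response variable only as one that "denotes any dichotomous efficacy parameter" and sets no event level. In SAP 6.4.1, by contrast, the logistic code carries DESCENDING and the notes define 1 as a responder.

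**The concern.** An LSMEANS request on treatment alone, in a model with a treatment-by-visit interaction, averages over visits. The text promises visit-specific effects, and neither document defines a visit-averaged effect as a parameter. A programmer who copied the line would obtain a plausible table of differences, CIs and p-values for a quantity that the plan does not name. There would be no error message to show the mismatch. A reader could take the figure as the Week 16 effect.

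Two further details affect the output. With TYPE=UN and no repeated effect named, a subject's rows are matched to covariance positions by their order. If a missed visit has no row, the later visits move into the wrong positions. In the GEE, with neither the coding of the response nor the event level stated, the direction of the odds ratio depends on a software default.

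**Working it through.** **Inputs.** There are three groups and two doses (SAP section 3). The visits are the SAP 5.2.2 list less Week 20 (follow-up) and EOT, both excluded by SAP 6.4.2. This leaves Weeks 2, 4, 8, 12 and 16. The plan states no figure to reproduce here, and the documents give no effect sizes.

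**1. What the line returns.** Let d(v) be the dose-minus-placebo difference at visit v. LSMEANS on `<TRTn>` weights the visits equally, so the reported difference is

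D = [d(2) + d(4) + d(8) + d(12) + d(16)] / 5.

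PDIFF on three groups gives 3 pairs: 2 dose-versus-placebo and 1 dose-versus-dose. The text promises 2 x 5 = 10 dose-versus-placebo differences, and none of them is printed. The MODEL statement has no SOLUTION option, so they cannot be assembled from printed coefficients either.

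**2. Check of the identity.** A treatment-by-visit mixed model was fitted to simulated data (3 x 50 subjects, some visits missing, a random intercept in place of TYPE=UN):

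- Lower dose, by visit: -5.79, -5.45, -12.81, -19.17, -23.45. Mean -13.33; main-effect LS-mean difference -13.33.
- Higher dose, by visit: -5.96, -0.31, -18.33, -22.13, -37.26. Mean -16.80; main-effect LS-mean difference -16.80.

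These figures confirm the algebra only. They say nothing about the size of effect in this trial.

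**3. How far D can lie from the Week 16 effect.** All profiles are assumptions.

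| Assumed effect at Weeks 2, 4, 8, 12, 16 | D | D / Week 16 |
|---|---|---|
| Constant: 20 throughout | 20 | 100% |
| Early plateau: 15, 25, 30, 30, 30 | 130/5 = 26 | 26/30 = 87% |
| Linear rise, proportional to 2, 4, 8, 12, 16 | 42/5 = 8.4 | 8.4/16 = 52.5% |
| Waning: 10, 20, 30, 30, 20 | 110/5 = 22 | 22/20 = 110% |
| Mixed: 10, 20, 20, 20, 30 | 100/5 = 20 | 20/30 = 67% |

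In the last row D equals the effect at Weeks 4, 8 and 12, which shows agreement by coincidence. For any non-negative effect that never declines, D lies between one fifth of the Week 16 effect (effect at Week 16 only) and all of it (constant effect), that is, 20% to 100%.

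**4. What the corrected request returns.** There are 3 x 5 = 15 treatment-by-visit cells, so 15 x 14 / 2 = 105 pairwise differences. Of these, 5 x 3 = 15 are within a visit: 10 dose-versus-placebo and 5 dose-versus-dose. The other 90 cross visits and are not wanted.

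**5. GEE.** With the interaction in the model, the treatment coefficient is the log odds ratio at the reference visit only. At any other visit the log odds ratio is the treatment coefficient plus the interaction coefficient, and its CI also needs their covariance. The sample code requests none of this. Changing the reference visit re-labels the coefficients and leaves every within-visit odds ratio unchanged.

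**The case against.** The strongest reply is that the plan already fixes the output. The prose states the at-visit difference and odds ratio, both models contain the interaction needed, and the code is labelled a sample. The table shells are in a separate document (SAP 10.2), so one cannot tell from these documents what would have been tabulated. Descriptive statistics over time and profile graphs are also planned, and a visit-averaged table would look odd beside them. All of this stands, and it is why the point is minor. It does not remove the conflict: the only estimate that the MMRM code requests is not the one promised.

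Three stronger readings are tempting but not supported.

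- A reader might infer that the GEE code contradicts the text as the MMRM code does. It requests no estimate, so it is silent rather than contradictory.
- A reader might take the Week 0 reference visit in the GEE as an error, because SAP 5.2.4.2 derives PASI response only from Visit 3. It is untidy, but the choice of reference alters no within-visit odds ratio.
- A reader might cite the Itch NRS wording, "analyzed in an MMRM for weekly averages (by-visit only) as described above", as a further promise of at-visit contrasts. It more naturally says which weekly averages enter the model, since the following text separates visit-anchored averages from a week-by-week set.

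The five-visit count can also be questioned, because the GEE code names Week 0 and the Itch NRS text starts there. The SAP 5.2.2 list supports five visits, but SAP 6.4.2 does not say so outright.

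**Conclusion.** The mismatch is real and minor. As written, the MMRM sample code yields 2 visit-averaged dose-versus-placebo differences per parameter, in place of the 10 at-visit differences that SAP 6.4.2 and Protocol 3.8.4.2 promise. The averaged figure equals the effect at a given visit only if the effect is constant or by coincidence. Its distance from the Week 16 effect cannot be stated, because the documents give no onset curve; the percentages above are illustrations. The counts rest on five modelled visits.

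A reader might go further and conclude that the model is wrong or that the secondary results will be wrong. The documents do not support that: the model can produce the promised estimates, and the prose says which they are. In the GEE sample, the unset event level deserves correction because it decides the direction of the odds ratio. The missing output request and the Week 0 reference are tidy-ups.

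The scope is the model-based secondary results at Weeks 2 to 16. The primary CMH test, the EOT and Week 20 results, and the single-time-point binary analyses are unaffected.

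**What to change.** In the MMRM sample code:

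- Replace the LSMEANS line with a request on `<TRTn>*<visit>` with differences and 95% CIs. State that only the 10 within-visit dose-versus-placebo differences are reported.
- Name `<visit>` as the repeated effect, so that the TYPE=UN covariance stays aligned when a visit row is absent. The effect of this on the estimates has not been tested here.
- State that the modelled visits are Weeks 2, 4, 8, 12 and 16.

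In the GEE sample code:

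- Define `<SAPE>` = 1 as a responder and set 1 as the event level, matching SAP 6.4.1.
- Add the request for within-visit odds ratios versus placebo with 95% CIs.
- As a tidy-up, use a post-baseline reference visit.

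The cost is a few lines of SAP text and code before programming. No new data are needed, and alpha, sample size and the primary analysis do not change. The 10 contrasts per parameter add no comparisons beyond those the text already promises, and the plan makes no multiplicity adjustment for secondary parameters.
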